7.2. Subject Exclusion Criteria

The subjects who meet any of the following criteria will be excluded in the study.

- 1. Subject had an acute exacerbation of psychiatric symptoms requiring change in antipsychotic medication (with reference to drug or dose) within 3 months (90 days) before screening.
- 2. Subject has known or suspected carcinoma.
- 3. Subject has known presence or history of renal or hepatic insufficiency.
- 4. Subject has significant disease(s) or clinically significant finding(s) on physical examination determined by the Investigator to pose a health concern to the subject while on study.
- 5. Subject has a history or presence of clinically significant abnormal ECG (based on ECG central overread report) that may jeopardize the subject's safety to participate in this study, or a screening 12-lead ECG demonstrating any one of the following: heart rate (HR) > 100 bpm, QRS > 120 msec, QTcF > 450 msec, or PR > 220 msec.
- 6. Subject has known history of a severe reaction to a previous antipsychotic (in the Investigator's opinion), including up to 80 mg/day of oral lurasidone.
- 7. Subject has a history of drug-dependence as per DSM-IV-TR criteria during the six month period immediately prior to study entry.
- 8. Subject has known or suspected excessive alcohol consumption, (exceeding more than 4 drinks on any single day or more than 14 drinks per week; 1 drink = 5 ounces of wine or 12 ounces of beer or 1.5 ounces of hard liquor) within 6 months of the screening visit or a positive urine alcohol test at screening.
- 9. Subject answers "yes" to "Suicidal Ideation" Items 4 or 5 on the C-SSRS at screening (in the past 1 month [30 days]) or at any point prior to randomization or history of suicidal behavior within the last two years.
- 10. Subject has significant orthostatic hypotension at screening (ie, a drop in systolic blood pressure of 30 mmHg or more and/or drop in diastolic blood pressure of 20 mmHg or more on standing).

- 11. Subject has presence or history (within the last year) of a medical or surgical condition that might interfere with the absorption, metabolism, or excretion of administered Lurasidone injectable suspension.
- 12. Subject has a history of epilepsy or risk of having seizures.
- 13. Subject has a positive urine alcohol at screening or on Day -12.
- 14. Subject has positive test results within 28 days prior to the start of the study for:
 - a. Human immunodeficiency virus (HIV).
 - b. Hepatitis B surface antigen and Hepatitis C antibody.
 - c. Urine drug test (marijuana, amphetamines, barbiturates, cocaine, opiates, benzodiazepines, methadone, or other drugs of abuse). However, a positive test for benzodiazepines may not result in exclusion of subjects if the Investigator determines that the use of a prescription benzodiazepine is appropriate.
 - d. Serum β -human chorionic gonadotropin (HCG) consistent with pregnancy (females only).
- 15. Subject has used of any inhibitor or inducer of CYP3A4 taken within 28 days prior to drug administration and until discharge.
- 16. Subject has have used of concomitant medications that prolong the QT/QTc interval within 28 days prior to Day -12 through follow-up.
- 17. Subject has received depot neuroleptics unless the last injection was at least one treatment cycle before Day -12.
- 18. Subject has poor peripheral venous access or does not tolerate venipuncture that would cause difficulty for collecting blood samples.
- 19. Subject has experienced significant blood loss (≥ 473 mL) or donated blood within 30 days prior to screening, or intends to donate plasma or blood or undergo elective surgery during study participation or within 30 days after the last study visit.
- 20. Subject has a prolactin concentration greater than or equal to 200 ng/mL at screening.
- 21. Subject is unwilling to abstain from vigorous exercise from Day -12 until study discharge.
- 22. Subjects has a significant risk of violent behavior or a significant risk of suicidal behavior based on history or in the PI's judgment OR is considered by the Investigator to be at imminent risk of suicide or injury to self, others, or property.
- 23. Subject has a history of allergic reaction (clinically relevant history of drug hypersensitivity) or has a known or suspected sensitivity to any substance that is contained in the study drug or to Polysorbate 80, sodium chloride, or sodium phosphate.
- 24. Subject requires treatment with a drug that consistently prolongs the QTc interval (see Section 22, Appendix IV).
- 25. Subject is currently participating, or has participated in a study with an investigational or marketed compound or device within 30 days prior to signing the informed consent, or

has participated in 3 or more studies within 18 months prior to signing the informed consent.

- 26. Subject is a staff member or the relative of a staff member.
- 27. Subject, in the Investigator's opinion, is unsuitable in any other way to participate in the study.
- 28. Subject is unable or unwilling to comply with study instructions, procedures or restrictions.

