9.5.1. Prior Medications

All prior antidepressants and mood stabilizers (eg, lithium, divalproex/valproic acid, carbamazepine) must be discontinued as tolerated and clinically appropriate starting on Day -12. All other psychotropic medication (except as described in Section 9.5.3), including antipsychotic medication, must be discontinued as tolerated and clinically appropriate starting on Day -12 in a manner that is consistent with labeling recommendations and conventional medical practice.

These prior medications will not be allowed until subjects have completed Day 30.

Initiation of new psychotherapeutic interventions (eg, a new course of psychotherapy) will not be permitted during the study through the restabilization period. Subjects who have participated in ongoing psychotherapy treatment for at least 12 weeks prior to screening will be permitted to continue this treatment during the study.

Additional medication use as specified in the exclusion criteria is prohibited prior to the study.

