Medications used for the as-needed treatment of anxiety/agitation and insomnia (eg, lorazepam and zolpidem) should not be used in close temporal proximity (defined as administration within 2 hours of each other). When lorazepam or zolpidem or other specified medications are not available, another similar agent at equivalent doses will be permitted as specified by the Medical Monitor. Opiates may be allowed in rare cases for a limited period of time with prior authorization from the Medical Monitor. Subjects who require treatment with one or more of the medications listed in Section 22, Appendix IV or Section 23, Appendix V should be excluded or discontinued (as appropriate) from the study. Since these lists of drugs are not comprehensive, Investigators should use medical judgment when a subject presents with a medication not on the list or consult with the Medical Monitor for clarification.

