9.5.4. Prohibited Medications

In accordance with the approved product labeling for Latuda (see approved product labeling), lurasidone should not be used concomitantly with a strong CYP3A4 inhibitor (eg, ketoconazole, clarithromycin, ritonavir, voriconazole, mibefradil). Lurasidone should not be used concomitantly with a strong CYP3A4 inducer (eg, rifampin, avasimibe, St. John's wort, phenytoin, carbamazepine). A list of strong CYP3A4 inhibitors and inducers included in Section 23, Appendix V).

The use of herbal supplements or other complementary or alternative medications during the trial is not permitted.

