10.1. Demographics and Baseline Characteristics

Subject self-report will be acceptable for listing all prior and concomitant medication use, demographics, medical history, psychiatric history, and evaluation for inclusion/exclusion except where specific protocol procedures are mandated to ensure appropriate enrollment (eg, certain baseline laboratory values). All medications taken within the 30 days before screening will be recorded.

Demographics (date of birth, sex, ethnicity, race), prior and current medications, and medical and psychiatric history will be collected.

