10.5.2.3. Day -8 (End of Washout/Taper Period)

The following study related procedures will be performed:

- Awaken Subject.
- Provide Meals.
- Review Inclusion/Exclusion Criteria.
- Perform Physical Examination.
- Record Weight and BMI.
- Obtain Vital Signs.
- Perform 12-Lead ECG.
- Collect Blood and Urine Samples for Clinical Laboratory Tests:
 - Hematology
 - Serum Chemistry
 - Urinalysis

- Lipid Panel
- Thyroid Panel
- Coagulation Panel
- Collect Blood Sample for Serum Prolactin.
- Collect Blood Sample for b-hCG Serum Pregnancy Test (female subjects).
- Collect Urine Sample for:
 - Urine Drug Screen
 - Urine Alcohol Test
- Administer C-SSRS (Since Last Visit version; pre-oral dose assessment).
- Record Concomitant Medications.
- Record Pretreatment Events.
- Subjects will fast for 8 hours before receiving study drug on Day -7.

10.5.3. Treatment/Observation Period, Days -7 to 28

Subjects are required to be inpatient until at least Day 15.

Dosing with oral lurasidone tablets to ensure subjects are able to tolerate treatment with lurasidone will occur on Day -7 and Day -6 (single oral lurasidone 80 mg dose each day).

Safety monitoring and washout of oral lurasidone will occur until Day -1.

Subjects who tolerate oral lurasidone will be randomized on Day 1 to either lurasidone or placebo injection. Safety monitoring and observation (including assessment of the injection site) as well as PK and pharmacodynamic assessments during the inpatient period will occur from Day 1 through Day 15.

Subjects may be discharged on Day 15 if in the Investigator's opinion the subject is clinically stable.

Subjects may remain inpatient at the Investigator's discretion up to Day 33.

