23. APPENDIX V. ADDITIONAL RESTRICTED SUBSTANCES

CYP3A4 Inducer	CYP3A4 Inhibitor
Carbamazepine	Amiodarone
Phenobarbital	Cimetidine
Phenytoin	Clarithromycin
Pioglitazone	Diltiazem
Rifabutin	Erythromycin
Rifampin	Fluvoxamine
St John's Wort	Grapefruit and grapefruit juice
	Indinavir
	Itraconazole
	Ketoconazole
	Mibefradil
	Nefazodone
	Nelfinavir
	Ritonavir
	Verapamil
	Troleandomycin

This is not an all-inclusive list of restricted enzyme inducers and inhibitors.

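### Section 9.5.1 and the Synopsis give carbamazepine a Day -12 stop, although exclusion 15 bars any CYP3A4 inducer for 28 days before dosing

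*Protocol*

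**What the plan says.** Exclusion 15 in protocol Section 7.2 reads: "Subject has used of any inhibitor or inducer of CYP3A4 taken within 28 days prior to drug administration and until discharge". It covers inhibitors and inducers of any strength. It does not say which administration or which discharge is meant.

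Section 9.5.1 says: "All prior antidepressants and mood stabilizers (eg, lithium, divalproex/valproic acid, carbamazepine) must be discontinued as tolerated and clinically appropriate starting on Day -12". The Synopsis, under prior and concomitant medications, repeats the sentence word for word.

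Section 9.5.4 closes its examples of strong inducers, and points to the appendix, with: "phenytoin, carbamazepine). A list of strong CYP3A4 inhibitors and inducers included in Section 23, Appendix V". Carbamazepine is the first entry in the inducer column of Appendix V, which adds: "This is not an all-inclusive list of restricted enzyme inducers and inhibitors".

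Other provisions bear on which rule governs:

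- Section 9.5.1 later says: "Additional medication use as specified in the exclusion criteria is prohibited prior to the study".
- Section 9.5.3 says that subjects who need drugs "listed in Section 22, Appendix IV or Section 23, Appendix V should be excluded or discontinued (as appropriate) from the study".
- Section 10.1 says: "All medications taken within the 30 days before screening will be recorded".
- Section 10.5.2.3 lists "Review Inclusion/Exclusion Criteria" among the Day -8 procedures.

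**The concern.** The Day -12 sentence names three example drugs. One of them is a drug that exclusion 15 keeps out of the study unless it was stopped at least 28 days before dosing. A coordinator who follows Section 9.5.1 or the Synopsis for a subject on carbamazepine would start the taper far too late to satisfy exclusion 15.

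Two things could follow:

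- **Missed at Screening, caught on Day -8.** The subject has come off a mood stabilizer for a study that he or she cannot enter. Table 2 schedules eligibility review at Screening and on Day -8. The Day -12 procedures in Section 10.5.2.1 begin the taper without one.
- **Missed at both.** The subject is dosed inside the sponsor's own washout window. That could affect Cmax and AUC, which are primary PK parameters, and the exposure data that the Safety Review Team uses for escalation. Failing an eligibility criterion is a potential important deviation under SAP Section 10. If it is confirmed, SAP Section 6.2 removes the subject from the PK population, and a dose group of 6 active subjects falls to 5.

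**Working it through.** The plan states no figure to reproduce. The check is a day count.

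**Inputs**

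- Washout required by exclusion 15: 28 days.
- Day on which discontinuation begins: Day -12 (Section 9.5.1 and Synopsis).
- Earliest stated taper start: Day -19 (Section 10.5.2.1).
- First oral dose: Day -7. Injection: Day 1 (Section 9.1).
- Day convention: SAP Section 7.1 has no Day 0, so Day -1 is the day before Day 1.
- Post-injection serum samples: 2, 4, 6, 12, 24, 48, 72, 96, 120, 144, 336, 504, 672 and 1440 h, 14 in all (Appendix III).

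**Days off drug if use ended on the stated day**

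- Day -12 to Day 1: 12 days; 28 - 12 = 16 short.
- Day -12 to Day -7: 5 days; 28 - 5 = 23 short.
- Day -19 to Day 1: 19 days; 28 - 19 = 9 short.
- Day -19 to Day -7: 12 days; 28 - 12 = 16 short.

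These figures describe the stated days and are not bounds. Day -12 is when discontinuation starts, so a last dose after a taper could fall later. Table 2 footnote h also lets some tapers start earlier.

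**Where the cut-off falls**

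- Anchored to the first oral dose: 28 days before Day -7 is Day -35, the first day of the screening window.
- Anchored to the injection: 28 days before Day 1 is Day -28, which is 16 days before Day -12.

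Both cut-offs precede Day -12 and Day -19. The anchors differ by 7 days.

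**Which anchor the text supports**

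- For Day -7: Section 11.1.1 ends the pre-treatment period at drug administration, and Section 10.2.1 places that point at the first tablet on Day -7.
- For Day 1: Section 11.3 starts AE recording after a first study drug dose on Day 1, and SAP Section 7.1 takes the injection day as the reference date.

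The text does not settle the choice.

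**What lies after discharge**

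Section 10.5.4 requires all subjects to be inpatients on Days 29 to 33. On the natural reading, final discharge is therefore Day 33, (33 - 1) × 24 = 768 h after the injection. Only the 1440 h sample, 1 of 14, comes later. Day 33 to Day 61 is 28 days.

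**The case against.** The strongest reply is that nothing conflicts in operation. Section 7 decides who enters. Section 9.5.1 tells sites how subjects already eligible come off psychotropics, and it defers to the exclusion criteria. The parenthesis illustrates drug classes and does not grant permission to enroll. Section 9.5.3 excludes subjects who need Appendix V drugs, Section 9.5.4 names carbamazepine as not to be combined with lurasidone, and medications are recorded at Screening and again from Day -12 to Day -8. A single site would have to overlook a named drug repeatedly.

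Most of this stands, and it limits the point to a drafting error with a contained risk. It does not remove the error. The deferring sentence is absent from the Synopsis passage. Section 9.5.3 turns on whether a subject requires the drug, which a site already tapering it could deny. Section 10.1 accepts self-report for medication history.

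A reader might infer three stronger things that the documents do not support:

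- **That the two rules cannot both be obeyed, or that the plan admits subjects on carbamazepine.** Both can be obeyed: such subjects are excluded, and the example is then redundant.
- **That exposure will be biased by some amount.** The documents give no figure for residual induction.
- **That ending the bar at discharge leaves 3 of 14 samples uncovered.** That requires a Day 15 discharge to end the bar (leaving 504, 672 and 1440 h), although the subject is readmitted on Day 29. Sections 9.5.2 to 9.5.4 also restrict most of these drugs later.

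Nor is an excluded profile lost beyond remedy. Section 6.2.1 adds subjects automatically only when fewer than 6 in a cohort complete Day 29, but it also allows dose levels to be repeated and cohorts added.

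**Conclusion.** The point holds as a wording error worth correcting. The Day -12 instruction is wrong for carbamazepine: it begins 12 days before the injection and 5 before the first oral dose, against a required 28. Exclusion 15 prevails on a strict reading, so harm arises only if a site takes Section 9.5.1 or the Synopsis as permission and Screening does not catch it. The consequence would then be a needless taper or, if Day -8 also misses it, one PK profile inside the washout window. Loss of that profile further depends on the deviation being confirmed as important.

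The missing anchor day in exclusion 15 is a lesser ambiguity worth 7 days of eligibility. The open end point is minor. The day counts assume SAP Section 7.1's convention and take the stated days at face value.

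**What to change.** 1. Delete carbamazepine from the examples in Section 9.5.1 and the Synopsis, and add in both places: *Appendix V agents follow exclusion 15, not the Day -12 stop.* The added sentence covers any other Appendix V agent that falls under the same instruction.
2. As a clarification, name the anchor day in exclusion 15. Day -7 is the conservative choice because it protects both the oral test doses and the injection. Day 1 is also defensible on the text.
3. Optionally, extend the end of exclusion 15 from discharge to the last PK sample on Day 61.

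The first change is protocol wording only, needs no SAP change, and removes no subject whom exclusion 15 does not already bar. The second, if set at Day -7, also excludes subjects whose last use fell between Day -35 and Day -28, whom a Day 1 reading would admit. The third has a real cost. Exclusion 15 covers any inhibitor or inducer, whereas Section 9.5.4 covers strong ones, the CYP3A4 clause in Section 9.5.2 attaches to short-term treatments, and Section 9.5.3 concerns the listed drugs and leaves unlisted ones to judgment. Extending the bar would newly restrict weaker or unlisted agents for 28 days after a Day 33 discharge, when subjects are back on their prior medications, to protect one sample.

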8. STUDY DRUG MATERIALS AND MANAGEMENT

8.1. Description of Study Drug

Reference Therapy Lurasidone 80 mg will be provided as film-coated tablet formulation as commercially available Latuda 80 mg tablets.

Lurasidone injectable suspension will be provided as sterile white to off-white aqueous suspension (150 mg/mL lurasidone) for intramuscular injection. The suspension will be packaged in clear USP Type I glass vials with rubber stoppers.

A starting dose of 30 mg (0.2 mL lurasidone injectable suspension) will be given. Lurasidone injectable suspension will be administered to subjects using syringe and gauge 22-23 needle. The syringe will be covered to maintain blinding.

Doses of 75, 150, 300, and 450 mg may be administered (ie, cohorts 2-5).

Placebo injection will be provided as sterile clear aqueous solution for intramuscular injection. The solution will be packaged in clear USP Type I glass vials with rubber stoppers.

Placebo for lurasidone injectable suspension will be administered to subjects using syringe and gauge 22-23 needle. The syringe will be covered to maintain blinding.

Table 5: Investigational Product

Attribute	Investigational Product		
Product name	Lurasidone Injectable Suspension 150 mg/mL	Placebo Injection 150 mg/mL	
Dosage form	Injectable suspension	Injectable solution	
Route of administration	Intramuscular injection	Intramuscular injection	
Physical description	Sterile white to off-white aqueous suspension	Sterile clear aqueous solution	
Excipients	Polysorbate 80, sodium chloride, monobasic sodium phosphate and dibasic sodium phosphate, and Water for Injection		

8.2. Study Drug Packaging and Labeling

8.2.1. Package Description

Reference therapy Lurasidone 80 mg film-coated tablets will be packaged in HDPE bottles as market product of Latuda $^{\text{\tiny \$}}$.

Lurasidone injectable suspension will be packaged, with pre-filled volume of 1.25 mL, in a clear USP Type I glass vials with rubber stoppers and sealed. The vials will be stored in a carton with dividers.

Placebo for Lurasidone injectable suspension will be packaged with pre-filled volume of 1.25 mL, in a clear USP Type I glass vials with rubber stoppers and sealed. The vials will be stored in a carton with dividers.

8.2.2. Labeling Description

All labeling and packaging for study drug will be based on all applicable regulatory requirements described in the United States (US) Code of Federal Regulations (CFR), CRF21, Part 312.6. Label text may include, but is not limited to, the following information:

- Protocol number
- Sponsor's name and address
- Contents (eg number of tablets, strength)
- Instructions for use and storage
- Lot number
- Unique medication number (if needed)

8.3. Study Drug Storage

Lurasidone oral tablets are to be stored at 25°C (77°F); excursions permitted to 15° - 30°C (59° F to 86°F).

Lurasidone injectable suspension and placebo for injection are to be stored at 20-25°C (68-77°F).

8.4. Dispensing of Study Drug

Unblinded clinical site pharmacist will prepare and quality check each injection dose for each subject per provided pharmacy manual, randomization schedule, and other applicable local regulations as set forth in the protocol. The unblinded site pharmacist will be trained with the pharmacy manual.

8.5. Study Drug Accountability

The Investigator or designee is responsible for storing the drug in a secure location and for maintaining adequate records of drug receipt and disposition that includes the dates, quantity, and use for purposes or by subjects. If the study is stopped for any reason or completed, all unused supplies of drug will be returned to the Sponsor, unless other instructions are provided in writing by Sponsor/CRO.

Upon receipt of study drug, the Investigator or designee will inventory and verify receipt of supplies. The site will perform an acknowledgement of receipt via site established process and per requirements outlined in the pharmacy manual confirming the date of receipt, inventory and condition of study drug received into site source document.

The Investigator or designee will maintain the inventory for accountability, including study drug dispensation, return and availability of study drug received. Established site standards and instructions outlined in the pharmacy manual will provide instruction for the accountability of the study drug at the clinical site.

The drug will not be dispensed to any person who is not a study subject under this protocol.

8.6. Study Drug Handling and Disposal

The Investigator or designee on an ongoing basis must maintain a drug inventory record of supplied, received, dispensed, and returned medication. The Investigator or designee is required to return all unused study drug to the Sponsor or designee, or destroyed as instructed in writing from Sponsor. The Investigator or designee is required to maintain copies of medication shipping receipts, drug accountability records, and records of return or final disposal of the study drug in accordance with local regulatory requirements.

